5.1 Overall Study Design

This is a Phase 1, randomized, observer-blind, placebo-controlled, dose-ranging study to evaluate the safety, tolerability, and immunogenicity of Zika vaccine mRNA-1893 administered to healthy flavivirus-seropositive and seronegative adult participants (18 to

Protocol mRNA-1893-P101

49 years of age, inclusive). A total of 120 participants (30 participants per cohort) will be enrolled into 1 of 4 mRNA-1893 dose cohorts (10, 30, 100, or 250 μg). Within each cohort, eligible participants will be randomly assigned to mRNA-1893 or placebo (4:1 mRNA-1893 to placebo) and administered the study vaccine as an intramuscular injection on a 2-dose vaccination schedule, 28 days apart (Day 1 and Day 29). Participants will be stratified by baseline flavivirus serostatus (seropositive and seronegative).

The study will comprise a Screening Phase (up to 28 days), a Vaccination Phase (up to 57 days), and a Long-Term Follow-up Phase (up to 12 months after last vaccination). Participants will have approximately 8 clinic visits with an additional 13 safety telephone calls. Study duration will be approximately 13 months for each participant. Participants will provide written informed consent before any study-specific procedures are performed.

Study vaccine dosing will begin with Cohort 1 (10 μ g mRNA-1893 or placebo), followed sequentially by Cohort 2 (30 μ g mRNA-1893 or placebo), Cohort 3 (100 μ g mRNA-1893 or placebo), and Cohort 4 (250 μ g mRNA-1893 or placebo).

For each dose cohort (Cohort 1 through 4), Safety Oversight will be performed 7 days after the first 5 participants (all seronegative) are randomly assigned and receive the first study vaccination (Day 1). Once safety is confirmed, the remaining 25 participants in the dose level cohort will be randomly assigned to dosing. Seven days after all 30 participants in the cohort have received the first study vaccination, a blinded internal safety team (IST) that is not directly involved in the day-to-day activities of the study, will review all available safety data for the currently dosed cohort and any cumulative safety data of all cohorts as the trial advances to determine the acceptability to escalate to the next mRNA-1893 dose level. The 30 participants in the first cohort will continue to receive their second study vaccine dose on Day 29 (+7 days).

[figure not shown]
The blinded IST will oversee the safety of the trial and will review safety data to ensure adherence to the protocol, will monitor safety laboratory test results and reactogenicity, and may request input from the safety monitoring committee should the study meet pause rules or for any other study events that could potentially affect participant safety. The IST will approve escalation to the next higher dosing cohort after review of blinded safety data of the currently dosed cohort through 7 days after the first vaccination and any cumulative safety data of all cohorts as the trial advances.

A diagram of the dosing schema by cohort is shown in Figure 1.

Protocol mRNA-1893-P101

Figure 1: Dosing Schema by Cohort

Figure 1: Dosing Schema by Cohort

Abbreviations: IST = internal safety team; S- = flavivirus seronegative; S+ = flavivirus seropositive.

Note: For each dose cohort (Cohorts 1 through 4), Safety Oversight will be performed 7 days after the first 5 participants (all flavivirus-seronegative) are randomly assigned and receive their first study vaccination (Day 1) before randomly assigning the remaining 25 participants in the cohort. Seven days after all 30 participants in the cohort have received the first study vaccination and review of all available safety data has been performed (ie, no safety concerns and pause rules have not been met), the IST will determine the acceptability to escalate to the next mRNA-1893 dose level.

5.2 Sample Size and Power

A total of 120 participants (30 participant per cohort) are planned for enrollment in the study and random assignment to study dosing. The sample size is considered sufficient to meet the study objective of identifying a dose and establishing initial safety results in a population of healthy adults in both endemic and nonendemic Zika regions. With 24 participants receiving mRNA-1893 in each dose level, there is a 92% probability to

Date Issued: 25May2021

observe at least 1 participant with an AE if the true incidence of the AE is 10% and a 70.8% probability if the true incidence of the AE is 5%.

5.3 Randomization

Participants will be randomly assigned (Day 1) in a blinded manner using the centralized Interactive Response Technology (IRT), with approximately 30 participants assigned to each cohort. Study vaccine dosing will begin with Cohort 1 (10 µg mRNA-1893 or placebo), followed sequentially by Cohort 2 (30 µg mRNA-1893 or placebo), Cohort 3 (100 µg mRNA-1893 or placebo), and Cohort 4 (250 µg mRNA-1893 or placebo). Within each cohort, participants will be randomly assigned in a blinded manner to receive either mRNA-1893 vaccine or placebo (4:1 mRNA-1893 vaccine to placebo) using the centralized IRT. Participants will be stratified according to flavivirus baseline serostatus.

In each cohort, the initial 5 participants (all seronegative) will be randomly assigned to vaccine or placebo (4:1 mRNA-1893 vaccine to placebo) before the remaining participants (n=25, 20 seronegative and 5 seropositive) are enrolled in the cohort.

Randomization by the centralized IRT will be in accordance with pre-generated randomization schedules, with only the unblinded pharmacy personnel having controlled access.

Dose group assignment in each cohort and stratification within each cohort is summarized in Table 1.

Protocol mRNA-1893-P101

Table 1: Dose Group Assignment

| | Dose Group | | | eus Status Tication ^a | Total | | |
|--------|------------|-----------|-----------|-------------------------------------|---------|--|--|
| Cohort | Assignment | n | Status | n | (Ratio) | | |
| | mRNA-1893 | 24 | + | 4 | | | |
| 1 | 10 μg | 24 | - | 20 | 30 | | |
| 1 | Placebo | 6 | + | 1 | (4:1) | | |
| | Placebo | 0 | - | 5 | | | |
| | mRNA-1893 | 24 | + | 4 | | | |
| 2 | 30 μg | 24 | - | 20 | 30 | | |
| 2 | Placebo 6 | 6 | + | 1 | (4:1) | | |
| | | riacedo 6 | - | 5 | | | |
| | mRNA-1893 | 24 | + | 4 | | | |
| 3 | 100 μg | 24 | - | 20 | 30 | | |
| 3 | Dlasaka | 6 | + | 1 | (4:1) | | |
| | Placebo | 6 | - | 5 | | | |
| | mRNA-1893 | 24 | + | 4 | | | |
| 4 | 250 μg | 24 | - | 20 | 30 | | |
| 4 | DI 1 | - | + | 1 | (4:1) | | |
| | Placebo | 6 | - | 5 |] | | |
| | | | Total 120 | | | | |

Abbreviations: - = flavivirus seronegative; + = flavivirus seropositive.

5.4 Blinding and Unblinding

This is an observer-blind study. The investigator, study participants, site monitors, and study staff will be blinded to the study vaccine administered until trial end, with the following exceptions:

Unblinded pharmacy personnel (of limited number) will be assigned to vaccine
accountability procedures and will prepare and administer mRNA-1893 (or
placebo) to all participants. The designee(s) will have no study functions other than
study vaccine management, documentation, accountability, preparation, and
administration. They will not be involved in participant evaluations and will not

In each cohort, the initial 5 participants enrolled will be flavivirus seronegative and randomly assigned to vaccine or placebo (4:1 mRNA-1893 to placebo) before the remaining participants (n=25, 20 seronegative and 5 seropositive) are enrolled in the cohort.

Protocol mRNA-1893-P101

reveal the study vaccine identity to either the participant or the study site personnel involved in the conduct of the study unless this information is necessary in the case of an emergency.

- An unblinded study monitor, not involved in other aspects of monitoring, will be
 assigned as the vaccine accountability monitor. They will have responsibilities to
 ensure that the site is following all proper vaccine accountability, preparation, and
 administration procedures.
- An unblinded statistician will provide a descriptive analysis of safety and immunological endpoints after the completion of each dosing cohort (refer to Section 7.8 for interim analyses), and perform evaluation of the pause rules criteria summarized in Table 3, Section 3.4.2.2 of the protocol.

6 Analysis Sets

The following analysis sets are defined: All Enrolled Participants Set, Intent-to-Treat (ITT) Set, Safety Set, and Per-Protocol (PP) Sets.

6.1 Analysis Sets for Safety

For the safety analysis sets described here, participants will be analyzed according to the vaccine received, rather than the vaccine to which the participant may have been randomly assigned.

The analyses of solicited safety data will be based on the Solicited Safety Sets; all other Safety analyses will be based on the Safety Set unless specified otherwise.

6.1.1 All Enrolled Participants Set

The All Enrolled Participants Set includes all participants who signed the ICF and were not screen failures. The All Enrolled Participants Set will only be used for descriptive purposes.

6.1.2 Safety Set

The Safety Set consists of all participants who received at least 1 dose of study vaccine (mRNA-1893 or placebo).

6.1.3 Solicited Safety Set (Solicited Local and Systemic Adverse Reactions)

A Solicited Safety Set is defined for each vaccination. The First (Second) Vaccination Solicited Safety Set consists of all participants in the Safety Set who have received the first

Protocol mRNA-1893-P101

(second) study vaccination and have contributed any solicited AR data (local or systemic reactogenicity events) from the time of first (second) study vaccination through the following 7 days (Day 1 through Day 8 for first vaccination and Day 29 through Day 36 for second vaccination).

The Solicited Safety Sets will be used for the analyses of solicited AEs.

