3.5.2 Completion of Diary Card

At each vaccination visit (Day 1 and Day 29), study staff will provide a diary card to participants and training on its proper use. The participant will use the diary card for recording AE information; this information will be subject to potential change based on further questioning and/or follow-up by study staff.

Each participant will be instructed to complete the diary card to including the following:

- Solicited local and systemic reactogenicity AEs, as defined in Section 3.5.6, that
 occur on the day of each vaccine administration and during the 7 days after vaccine
 administration, with appropriate documentation to allow severity scoring by the
 investigator.
- Daily oral body temperature measurement should be performed at approximately the same time each day using the thermometer provided by the study site. If body

temperature is taken more than once in a given day, only the highest temperature reading should be recorded.

- Measurement, as applicable, for solicited local AEs; the size measurements will be performed using the ruler provided by the study site.
- All medications (excluding vitamins and minerals) taken on the day of each vaccine administration and during the 28 days after vaccine administration.
- Any unsolicited AE (Section 3.5.7) during the 28 days after each vaccine administration

During clinic visits, study staff will review the diary card information regarding solicited and unsolicited AEs, body temperature, and concomitant medications. This information will be recorded in the participant's source documents and the eCRF.

Diary cards will be the only source documents allowed for solicited systemic and local AEs (including body temperature measurements). The following additional rules apply to documentation of safety information collected using Diary Cards:

- No corrections or additions to the Diary Card will be allowed after it is delivered to the site.
- Any blank or illegible fields on the Diary Card must be described as missing data.
- The site staff must enter all readable entries in the Diary Cards into the eCRF.
- Any new safety information reported during the site visit (including a solicited reaction) must not be written into the Diary Card and must be described in the source documents as verbally reported event. Any adverse reaction reported in this manner must be described as an unsolicited reaction and therefore entered on the adverse event eCRF.

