3.6.7 Handling of Missing Data

For GMT calculation, antibody values reported as below the lower LOQ (LLOQ) will be replaced by $0.5 \times \text{LLOQ}$. Values that are greater than the upper LOQ (ULOQ) will be converted to the ULOQ. Missing data will not be imputed.

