7.1 General Considerations

Participants will be identified in the listings by the participant identification number concatenated with the site number. For rescreened participants, only the data collected from the last screening will be presented in the data listings and included in the summaries.

Data from participants excluded from an analysis set will be presented in the data listings but not included in the calculation of summary statistics for the corresponding analysis set.

Although date of physical exam is collected in the eCRF, this data will not be presented in the data listings.

The following treatment groups will be used for summary purposes:

- Placebo
- mRNA-1893 10 μg
- mRNA-1893 30 μg
- mRNA-1893 100 μg
- mRNA-1893 250 μg
- mRNA-1893 Total

For categorical variables, frequencies and percentages will be presented. Continuous variables will be summarized using descriptive statistics (number of participants, mean, median, standard deviation [SD], minimum, and maximum). See Appendix B for variable display standards.

When count data are presented, the percentage will be suppressed when the count is zero in order to draw attention to the non-zero counts. A row denoted "Missing" will be included in count tabulations where specified on the shells to account for dropouts and missing values. The denominator for all percentages will be the number of participants in that treatment within the analysis set of interest, unless otherwise specified.

For the change from Baseline safety summaries, Baseline will be defined as the last non-missing measurement (including repeated and unscheduled assessments) before the first vaccination.

For the immunogenicity analyses, Baseline will be defined as the last non-missing assessment collected at Visit Day 1.

Study Day relative to the first vaccination will be calculated as below:

- Study Day prior to the first vaccination will be calculated as: date of assessment/event date of the first vaccination;
- Study Day on or after the date of the first vaccination will be calculated as: date of assessment/event date of the first vaccination + 1;

Study Day relative to the most recent vaccination will be calculated as below:

- Study Day prior to the first vaccination will be calculated as: date of assessment/event date of the first vaccination;

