The percentage of participants who report each individual solicited local AR and solicited systemic AR from the time of study vaccination through the following 6 days (Day 1 through Day 7 and Day 29 though Day 35) will be tabulated by grade (including grades 1, 2, 3, and any grade >0), treatment group as defined in Section 7.1, and vaccination (first or second). These summaries will also be presented separately for flavivirus seropositive and seronegative participants.

Date Issued: 25May2021

Duration (in days) of each solicited AR will be summarized by treatment group and vaccination.

All solicited ARs, local solicited ARs, systemic solicited ARs, solicited ARs that are still on-going 6 days after vaccination, and solicited rash events will be presented in separate data listings.

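### A participant with some solicited diary data but no usable entry for a given reaction stays in that reaction's denominator and counts arithmetically as a non-event.

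*SAP*

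**What the plan says.** The rule has to be assembled from several places.

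- **Who is in the set.** SAP 6.1.3 defines one Solicited Safety Set per vaccination. It takes participants who were vaccinated and "have contributed any solicited AR data (local or systemic reactogenicity events) from the time of first (second) study vaccination through the following 7 days", that is, through Day 8 or Day 36. No entry for any particular reaction is required. The section adds: "The Solicited Safety Sets will be used for the analyses of solicited AEs".
- **Denominator.** SAP 7.1: "The denominator for all percentages will be the number of participants in that treatment within the analysis set of interest, unless otherwise specified".
- **Numerator.** SAP 7.6.1 tabulates "The percentage of participants who report each individual solicited local AR and solicited systemic AR from the time of study vaccination through the following 6" (the number is in days; the window is given as Day 1 to 7 and Day 29 to 35). The results "will be tabulated by grade (including grades 1, 2, 3, and any grade >0"), by treatment group and vaccination, and again separately by flavivirus serostatus. No other denominator is named.
- **What a blank means.** Protocol 3.5.2: "Any blank or illegible fields on the Diary Card must be described as missing data". The same section makes the diary the only source for solicited events and closes it to additions once handed in. For a reaction mentioned verbally at the visit it says: "Any adverse reaction reported in this manner must be described as an unsolicited reaction and therefore entered on the adverse event eCRF".
- **Display of missing values.** SAP 7.1 provides for a Missing row in count tables where the table shells call for one. The shells are not part of the documents.

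**The concern.** The protocol treats a blank as unknown, but the percentage treats it as if the reaction did not happen. The SAP never labels it that way. The effect comes from pairing a denominator that needs any solicited entry with a numerator that needs an entry for that specific reaction. The gap cannot be closed later: a participant who left the field blank and then tells staff about the reaction is recorded on the unsolicited side and remains a non-event in the solicited table.

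The rates concerned are the first primary endpoint (SAP 4.1). The direction is the favourable one for a safety endpoint, since blanks can lower a reported rate but cannot raise it. The tables by serostatus are the most exposed, because each dose level has only 4 seropositive vaccinees planned.

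**Working it through.** **Inputs.** 24 vaccinees per dose level (Protocol 3.6.4, SAP 5.2), of whom 20 are seronegative and 4 seropositive (Table 1 in both documents). Placebo is pooled: 4 × 6 = 24. The number of blanks b, the event count x and the true rate p are assumed, because the documents give no missing-diary rate.

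**1. The plan's own figures.** The chance of at least one event among 24 is 1 − (1 − p)^24. At p = 10% this is 1 − 0.90^24 = 0.920, and at 5% it is 1 − 0.95^24 = 0.708. Both stated values (92% and 70.8%) reproduce. They do not bear on the denominator question.

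**2. Who is affected.** Three kinds of vaccinated participant can be told apart for a given reaction:

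| Diary for that vaccination | In denominator | Can enter numerator |
|---|---|---|
| No solicited entry at all | No | No |
| At least one usable entry for the reaction on a tabulated day | Yes | Yes |
| Some solicited entry, none usable for the reaction on a tabulated day | Yes | No |

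Only the third row is a problem.

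**3. Direction.** Let e of the b third-row participants have had the reaction, with 0 ≤ e ≤ b. The SAP reports x/N. Complete diaries would have given (x + e)/N. The reported rate is therefore at or below the complete-data rate, and equal to it only if e = 0.

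**4. Expected size if blanks are unrelated to the reaction.** The expected reported rate is p × (N − b)/N. With N = 24:

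| True rate | 1 blank (× 23/24) | 2 blanks (× 22/24) |
|---|---|---|
| 10% | 9.6% | 9.2% |
| 30% | 28.75% | 27.5% |
| 50% | 47.9% | 45.8% |
| 80% | 76.7% | 73.3% |

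**5. The same thing on observed counts.** Intervals are Clopper-Pearson, the SAP's method.

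| Case | SAP: x/N | Per-reaction: x/(N − b) | Every blank an event: (x + b)/N |
|---|---|---|---|
| N = 24, x = 12, b = 1 | 50.0% (29.1–70.9) | 12/23 = 52.2% (30.6–73.2) | 13/24 = 54.2% |
| N = 24, x = 12, b = 2 | 50.0% (29.1–70.9) | 12/22 = 54.5% (32.2–75.6) | 14/24 = 58.3% |
| N = 4, x = 2, b = 1 | 50.0% (6.8–93.2) | 2/3 = 66.7% (9.4–99.2) | 3/4 = 75.0% |

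The complete-data rate lies between the first and last columns. The SAP always reports the lower end of that range.

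**6. Window mismatch.** The set accepts entries through Day 8 or Day 36, but tabulation stops at Day 7 or Day 35. A participant whose only solicited entry falls on Day 8 or Day 36 is in every reaction's denominator with no chance of counting in any numerator. Whether such entries can exist depends on the card: Protocol 3.5.2 has solicited events recorded for 7 days after the vaccination day, while Protocol 3.5.6 and SAP 7.6.1 have 6.

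**The case against.** The best case against the point has five parts.

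- **The shells may deal with it.** SAP 7.1 allows a Missing row and another denominator where one is specified. The reference to grades above 0 suggests that grade 0 may be recorded separately from missing. This stands in part: a Missing row would let a reader see the blanks and recompute. Nothing in the text says that it would change the percentage, and no other denominator is given.
- **Blanks may be rare.** Diary training, review at visits, safety calls with reminders and requests for unreturned cards all work against them. Participants with no solicited data are already excluded, and anyone with a usable entry for the reaction can still be counted. This stands. A reader might infer that every solicited rate is biased downward; the documents do not support that, because the effect needs third-row participants to exist.
- **No imputation rule is clearly broken.** A reader might set the denominator against Protocol 3.6.7, "Missing data will not be imputed", and call it a contradiction. That sentence closes a paragraph on antibody values, and SAP 7.1 repeats the idea in the same setting. It is weak support; the blank-field rule in Protocol 3.5.2 is what carries the point.
- **Little hangs on the table.** The study is descriptive, and the proportional pause rules use their own denominator of exposed participants with safety data (notes to Protocol Table 3). This stands and limits the importance.
- **The remedy can err the other way.** If fields are left blank because nothing happened, dropping those participants raises the rate. This is also true, and is why the number without an entry should be shown.

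**Conclusion.** The point holds in a conditional form. As written, the SAP gives a solicited rate that is too low whenever participants with no usable entry for a reaction include some who had it. The size is unknown because the documents give no missing-diary rate. With one or two blanks among 24, and blanks unrelated to the reaction, the expected loss at a true 50% is 2.1 or 4.2 percentage points, against an interval of about 29% to 71% for 12 of 24. That is small. In the seropositive tables one blank among 4 moves 66.7% to 50.0%, although the intervals there are very wide under either denominator.

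A reader might also infer that dose comparisons are distorted because participants who feel unwell fill in their cards less completely. That is possible, but nothing in the documents shows it. The formula in step 4 would not apply in that case, because it assumes blanks unrelated to the reaction. The point is worth acting on because the correction is cheap and the rates are a primary endpoint, not because a material bias has been shown.

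**What to change.** Add to SAP 7.6.1 that, for each reaction and vaccination, the denominator is the number of Solicited Safety Set participants with at least one non-missing entry for that reaction in the tabulated window (Day 1 to 7 or Day 29 to 35). Print that n in each row and report how many set members had no entry. This uses the room that SAP 7.1 already leaves for a different denominator, and it also removes the Day 8 and Day 36 mismatch from the percentages.

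The cost is a sentence in the SAP and a per-row n in the tables; no new data and no change in conduct are needed. There are two drawbacks. Denominators will differ slightly between reactions, and a participant with only some days completed and no reaction on them still counts as a non-event. Showing the number without an entry lets a reader work out the range between x/N and (x + b)/N.
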